4.9.2 Deaths, Serious Adverse Events, and Other Significant Adverse Events

The following summaries will be provided by cohort and by MedDRA SOC and PT:

- SAEs
- Drug taken period SAEs
- Related SAEs to the study drug
- AEs leading to study discontinuation

• AEs leading to death

The following listings are to be provided:

- A by-subject listing of all deaths that occurred during the study
- A by-subject listing of all SAEs
- A by-subject listing of all AEs leading to discontinuation of study

4.9.3 Clinical Laboratory Evaluation

Descriptive statistics (for non-categorical data including hematology, coagulation function and blood chemistry) will be presented by cohort and time-point for both absolute values and changes from baseline.

Frequency tabulations of qualitative clinical laboratory variables (urinalysis) will be presented by cohort and time-point.

Shift tables will be presented for select laboratory parameters (Blood chemistry, coagulation function and hematology).

Laboratory values (hematology, coagulation, biochemistry and urinalysis) will be listed by subject and study time point, including changes from baseline (with the exception of urinalysis).

All values outside the clinical reference ranges will be flagged in the data listings. The abnormal values will be flagged with 'L' for values below the lower limit of the clinical reference range and 'H' for values above the upper limit of the clinical reference range and included in the listings. The Investigator will assess whether the values outside the clinical reference range are clinically significant and these will be reported as abnormal not clinically significant (NCS) or abnormal clinically significant (CS). Clinically significant laboratory values will be recorded by the Investigator as AEs.

4.9.4 Vital Signs, Physical Findings and Other Observations Related to Safety

Vital Signs

Descriptive statistics will be presented by cohort and time-point for absolute values and changes from baseline.

A by-subject listing of all vital sign measurements and change from baseline will be presented by cohort and time point.

ECG

Descriptive statistics will be presented by cohort and time-point for absolute values and changes from baseline.

A summary of the number and percentage of subjects with QTc exceeding some predefined upper limits (e.g. >450ms, >500ms, >520ms, >550ms for measured values as well as. >30ms, >60ms for changes from baseline) of ECG parameters will be displayed in a frequency table.

All ECG parameters will be listed by subject for each cohort and time point including changes from baseline.

The listing of ECG abnormality will be presented separately.

Physical Examination

The full physical examination includes an assessment of general appearance and a review of systems (general appearance, skin, head and neck, mouth, lymph nodes, thyroid, abdomen, and musculoskeletal, cardiovascular, neurological, and respiratory systems).

The brief physical examination includes an assessment of the cardiovascular and respiratory examinations.

Clinically significant physical exam findings will be listed.

4.10 Handling of Dropouts or Missing Data

No imputation of missing data will be performed except for partial dates imputation mention in Section 6.3.

4.11 Planned Interim Analysis

No interim analysis will be performed for this study.

4.12 Determination of Sample Size

No formal hypothesis testing will be conducted. The number of subjects in each cohort is expected to provide sufficient data to allow the assessment of the safety, tolerability and PK profile of mavacamten in Chinese subjects. Hence approximately 8-12 subjects will be enrolled in Phase I to obtain adequate PK and safety data based on China regulatory consideration.

4.13 Explanation for Inconsistency with Planned Analysis

In the study protocol, one of the laboratory biochemistry parameters collected is urea nitrogen, but since urea nitrogen is no longer applicable at the site, the item actually collected in the eCRF is urea. It is hereby stated that in this statistical analysis plan, urea nitrogen described in the protocol was changed to be urea, and indicators of urea actually collected were used for analysis.

In the study protocol, the pharmacokinetic analysis set (PKS) was defined as: The pharmacokinetic (PK) analysis set consists of all subjects exposed to mavacamten with at least one plasma drug concentration result.

In this analysis plan, the definition of pharmacokinetic analysis set (PKS) was additionally described. That subjects without serious protocol violations affecting PK parameter results were included in the analysis set was added to more accurately describe the PKS analysis set. The modified definition is as follows: The pharmacokinetic (PK) analysis set consists of all subjects exposed to mavacamten with at least one plasma drug concentration result and without serious protocol violations affecting PK parameter results. It is hereby stated.

REFERENCES 5

[1] SAS® Version 9.4 of the SAS System for Personal Computers. Copyright © 2002-2003. SAS Institute Inc. SAS and all other SAS Institute Inc. product or service names are registered trademarks or trademarks of SAS Institute Inc., Cary, NC, USA.

[2] Phoenix®WinNonlin® Professional Software Version 8.2. https://www.certara.com

Shanghai LianBio Development Co., Ltd. LB2001-101

Statistical Analysis Plan

6 APPENDICES

6.1 Schedule of Assessments

Table 2Study Flow Chart

Weeks	Pre-screening	Screening Period	In-l	iouse	Peri	od			C	Outpati	ent Pe	riod			End of study visit
Days	D-43 to D-15	D-14 to D-2	D-1	D1	D2	D3	D7	D10	D14	D21	D28	D35	D45	D60	D75
Visit Window (day)							±1	±1	±1	±1	±1	±1	±1	±1	±1
Signing the pre-screening ICF ¹	Х														
Demographics ²	Х														
CYP2C19 genotyping	Х														
Signing the main ICF		X													
Inclusion/exclusion criteria		X	Х												
Assign subject number	Х	X	Х												
Medical history		Х													
Vital signs ³		X	Х	Х	Х	Х	Х	Х	X	X	Х	Х	Х	X	Х
Physical examination ⁴		X	Х			Х									Х
Weight, height ⁵		Х													Х
12-lead ECG ⁶		X	Х	Х		Х					Х			X	Х
Echocardiography		X													
Hematology ⁷		X	Х								Х				Х
Blood chemistry ⁸		X	Х			Χ					Х				Х
Urinalysis ⁹		Х	Х								Х				X

TP-GDO-WW-133-02 Effective Date: 26 Nov 19 signature> Related to: SOP-GDO-WW-019 CONFIDENTIAL

Project Document Version No. 0.6

Project Document Effective Date: <Date of last

Page 26 of 33

Shanghai LianBio Development Co., Ltd. LB2001-101

Statistical Analysis Plan

Weeks	Pre-screening	Screening Period	In-l	house	Peri	od			C	Outpati	ent Pe	riod			End of study visit
Days	D-43 to D-15	D-14 to D-2	D-1	D1	D2	D3	D7	D10	D14	D21	D28	D35	D45	D60	D75
Visit Window (day)							±1	±1	±1	±1	±1	±1	±1	±1	±1
Coagulation ¹⁰		X	X			Х					Х				Х
FSH ¹¹		X													
Serum pregnancy test ¹²		X													Х
Urine Pregnancy test ¹²			Х								Х			X	
Hepatitis B, C, and HIV virology		x													
Alcohol or drug abuse test ¹³		X	Х												
Investigational drug ¹⁴				X											
PK blood sampling ¹⁵				X	Х	Х	Х	Х	X	X	Х	X	X	X	Х
Concomitant medications		X	Х	X	Х	Х	Х	Х	Х	X	Х	Х	Х	X	Х
AE ¹⁶	Х	X	Х	X	X	X	X	X	Х	Х	X	Х	Х	X	Х

Abbreviations: AE = adverse event; ALP = alkaline phosphatase; ALT = alanine aminotransferase; APTT = activated partial thromboplastin time; AST = aspartate aminotransferase; BP = blood pressure; CK = creatine kinase; CYP = cytochrome P450; ECG = electrocardiogram; EOS = end of study; FIB = fibrinogen; FSH = follicle stimulating hormone; HIV = human immunodeficiency virus; HR = heart rate; ICF = informed consent form; INR = international normalized ratio; PK = pharmacokinetic; PT = prothrombin time; QD = once daily; RBC = red blood cell; SAE = serious AE; TT = thrombin time; WBC = white blood cell. Note: Safety laboratory assessments (Hematology, Biochemistry, Coagulation test, Urinalysis) has no need to be repeated on Day -1 if latest results are within 7 days.

6.2 Schedule of PK Sampling

3mL whole blood will be collected at each following time point for PK analysis.

TP-GDO-WW-133-02 Effective Date: 26 Nov 19 signature> Related to: SOP-GDO-WW-019 CONFIDENTIAL

Project Document Version No. 0.6 Project Document Effective Date: <Date of last

Page 27 of 33

Shanghai LianBio Development Co., Ltd. LB2001-101

Statistical Analysis Plan

Blood samples will be obtained to determine mavacamten concentrations at pre-dose and 10min, 20min, 30min, 45min, 1h, 1.5h, 2h, 3h, 4h, 8h, 12h, 24h, and 48 hours after administration of mavacamten. Additional blood samples will be collected at Days 7, 10, 14, 21, 28, 35, 45, 60 and 75 (**Table 2**).

Table 2	PK Sampling Schedule
---------	----------------------

	In-ho	Outpatient Period								End of study visit		
Days	D 1	D 2	D 3	D 7	D 10	D 14	D 21	D 28	D 35	D 45	D 60	D 75
Visit												
Window	0	0	0	±1	±1	±1	±1	±1	±1	±1	±1	±1
(day)												
Collection time points	Pre-dose (within 60 min before dosing) 10 min±2 min 20 min±2 min 30 min±2 min 1 h±2 min 1 h±2 min 2 h±3 min 2 h±3 min 4 h±3 min 4 h±3 min 12 h±5 min	24 h ± 1 h post-dose	48 h ± 1 h post-dose	Outpatient visits: 144 h ± 24 h post-dose on Day 1	Outpatient visits: 216 h ± 24 h post-dose on Day 1	Outpatient visits: 312 h ± 24 h post-dose on Day 1	Outpatient visits: 480 h ± 24 h post-dose on Day 1	Outpatient visits: 648 h ± 24 h post-dose on Day 1	Outpatient visits: 816 h ± 24 h post-dose on Day 1	Outpatient visits: 1056 h ± 24 h post-dose on Day 1	Outpatient visits: 1416 h ± 24 h post- dose on Day 1	EOS Visit: 1776 h ± 24 h post-dose on Day 1

6.3 Imputation Rules for Partial Dates

Imputed dates will NOT be presented in the listings. In general, when calculating the relative study days, the imputation of the partial dates will be as follows:

Incomplete Start Date

TP-GDO-WW-133-02 Effective Date: 26 Nov 19 signature> Related to: SOP-GDO-WW-019 CONFIDENTIAL

Project Document Version No. 0.6 Project Document Effective Date: <Date of last

Page 28 of 33

Shanghai LianBio Development Co., Ltd. LB2001-101

Statistical Analysis Plan

- If only day is missing, date imputed will be 1st of the month.
- If both month and day are missing, January 1 will be imputed.

Incomplete End Date

- If only day is missing, date imputed will be last day of the month.
- If both month and day are missing, December 31 will be imputed.

Table and Table 3 present algorithm for imputing partial dates for drug taken period AE and prior/concomitant medication respectively.

Table 3Algorithm for Drug Taken Period Adverse Events:

Start/Increase Severity Date	Stop Date	Action
Known	Known	Considered as a drug taken period AE if start date on or after the date of the dose of investigational product (IP)
	Partial	Considered as a drug taken period AE if start date on or after the date of the dose of IP. The last day of the month and the last month (i.e., December) will be used if the stop day/month is missing.
	Missing	Considered as a drug taken period AE if start date on or after the date of the dose of IP
Partial, but known components show that it cannot be on or after first IP taken date	Known	Not a drug taken period AE. The first day of the month and January will be used if the start day/month is missing.

TP-GDO-WW-133-02 Effective Date: 26 Nov 19 signature> Related to: SOP-GDO-WW-019 CONFIDENTIAL

Project Document Version No. 0.6 Project Document Effective Date: <Date of last

Page 29 of 33

Shanghai LianBio Development Co., Ltd. LB2001-101

Statistical Analysis Plan

Start/Increase Severity Date	Stop Date	Action
	Partial	Not a drug taken period AE. The first day of the month and January will be used if the start day/month is missing. The last day of the month and the last month (ie, December) will be used if the stop day/month is missing.
	Missing	Not a drug taken period AE. The first day of the month and January will be used if the start day/month is missing.
Partial, could be on or after first IP taken date	Known	Considered as a drug taken period AE, if stop date is after first IP taken date. The first IP taken date will be used if start date is in the same month/year with first IP taken date, or the first day of the month and January will be used if the start day/month is after first IP taken date Considered as not drug taken period AE, if stop date is prior to first IP taken date. The first day of the month and January will be used if the start day/month is missing.
	Partial	Considered as a drug taken period AE. The first IP taken date will be used if start date is in the same month/year with first IP taken date, or the first day of the month and January will be used if the start day/month is after first IP taken date. The last day of the month and the last month (ie, December) will be used if the stop day/month is missing.
	Missing	Considered as a drug taken period AE. The first IP taken date will be used if start date is in the same month/year with first IP taken date, or the first day of the month and January will be used if the start day/month is after first IP taken date.

TP-GDO-WW-133-02 Effective Date: 26 Nov 19 signature> Related to: SOP-GDO-WW-019 CONFIDENTIAL

Project Document Version No. 0.6 Project Document Effective Date: <Date of last

Page 30 of 33

Shanghai LianBio Development Co., Ltd. LB2001-101

Statistical Analysis Plan

Start/Increase Severity Date	Stop Date	Action
Missing	Known	Considered as a drug taken period AE if stop date is on or after the date
		of the dose of IP.
	Partial	The last day of the month and the last month (ie, December) will be used
		if the stop day/month is missing. If the imputed stop date is on or after
		the dose of IP considered as a drug taken period AE; if the year is
		missing, considered as a drug taken period AE.
	Missing	Considered as a drug taken period AE

TP-GDO-WW-133-02 Effective Date: 26 Nov 19 signature> Related to: SOP-GDO-WW-019 CONFIDENTIAL

 Project Document Version No. 0.6

 Project Document
 Effective Date:
 <Date	of
 last

Page 31 of 33

Shanghai LianBio Development Co., Ltd. LB2001-101

Statistical Analysis Plan

Table 3 Algorithm for Prior/Concomitant Medications:

Start Date	Stop Date	Action
Known	Known	If stop date is prior to the date for the dose of IP, considered as prior; if stop date are on or after the
		date for the dose of IP, considered as concomitant.
	Partial	The last day of the month and the last month (ie, December) will be used if the day/month of stop date
		is missing.
		If the impuated stop date is prior to the date for the dose of IP, considered as prior; if the imputed stop
		date are on or after the date for the dose of IP, considered as concomitant.
	Missing	Considered as concomitant.
Partial	Known	The first day of the month and January will be used if the start day/month is missing.
		If stop date is prior to the date for the dose of IP, considered as prior; If stop date are on or after the
		date for the dose of IP, considered as concomitant.
	Partial	The first day of the month and January will be used if the start day/month is missing. The last day of
		the month and the last month (ie, December) will be used if the day/month of stop date is missing.
		If the imputed stop date is prior to the date for the dose of IP, considered as prior; If imputed stop date
		are on or after the date for the dose of IP, considered as concomitant.
	Missing	Considered as concomitant.
Missing	Known	If stop date is prior to the date for the dose of IP, considered as prior; if stop date is on or after the date
		for the dose of IP, considered as concomitant.

TP-GDO-WW-133-02 Effective Date: 26 Nov 19 signature> Related to: SOP-GDO-WW-019 CONFIDENTIAL

Project Document Version No. 0.6 Project Document Effective Date: <Date of last

Page 32 of 33

Shanghai LianBio Development Co., Ltd. LB2001-101

Start Date	Stop Date	Action
	Partial	The last day of the month and the last month (ie, December) will be used if the day/month of stop date
		is missing. If the imputed stop date is prior to the date for the dose of IP, considered as prior; if he
		imputed stop date is on or after the date for the dose of IP, considered as concomitant.
	Missing	Considered as concomitant.

TP-GDO-WW-133-02 Effective Date: 26 Nov 19 signature> Related to: SOP-GDO-WW-019 CONFIDENTIAL

 Project Document Version No. 0.6

 Project
 Document
 Effective
 Date:
 <Date	of
 last

Page 33 of 33

Statistical Analysis Plan

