7.2 Safety Assessments

Safety will be assessed throughout the study (**Table 1**). Safety assessments include physical examinations, vital signs, ECGs, observed and subject-reported AEs, and safety laboratory results.

Any abnormal findings judged by the investigator to be clinically significant will be recorded as an AE (See Section 8.1).

Physical Examination

Physical examinations will be conducted at screening Day-1, Day 3 and at the EOS Visit. A complete physical examination will be conducted at screening and the EOS Visit. An abbreviated physical examination will be conducted on Days -1 and 3 (**Table 1**).

A complete physical examination includes assessments of general appearance, skin, head and neck, mouth, lymph nodes, thyroid, abdomen, and musculoskeletal, cardiovascular, neurological, and respiratory systems. Brief physical examination included cardiovascular and respiratory examinations.

Height (cm) and body weight (kg) will be measured at screening, and BMI (kg/m²) will be calculated. Body weight (kg) will be measured at EOS.

Vital Signs

Vital signs will be assessed at each study visit and include temperature, HR, respiratory rate, and systolic and diastolic BP in a supine position after 5 minutes of rest (**Table 1**). While the

subject is in the CRU, vital signs will be taken upon rising in the morning. On Day 1, vital signs should be collected within 3 h before IMP dosing.

12-lead ECG

Twelve-lead ECG evaluations will be performed after 10 minutes of rest in the supine position at screening, Day -1, Day 1 (pre-dose, within 3 h before dosing, and at 2 h \pm 30 min post-dose), Day 3, Day 28, Day 60 and the EOS Visit (**Table 1**). Parameters to be evaluated include, but are not limited to: HR, rhythm, PR interval, QRS interval, QT interval, P wave, QRS complex, T wave morphology, ST segment displacement, etc.

The investigator will judge the overall interpretation as normal or abnormal with clinical significance or abnormal with no clinical significance. The investigator will review the ECG with any other clinical findings, subject's medical history, and laboratory data to determine the clinical significance of the findings.

The investigator may add extra 12-lead ECG safety assessments if there are any clinically significant abnormal findings or if the investigator considers it is required for any other safety reason. These assessments should be recorded as an unscheduled assessment.

Other Safety Assessments

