8.2 Collection and Reporting of AEs

8.2.1 Collection Time

AEs will be assessed from the time the subject signs pre-screening ICF through the end of the study. However, only study procedure related AEs (e.g., blood sampling) will be collected during the pre-screening and screening period.

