8.2.3 Start Date/Time and Stop Date/Time

The date (time, if applicable) that the AE started and the date (time, if applicable) that the event ended will be recorded. For events that continue for long periods of time, recording the end date as the day the event stabilized will also be acceptable.

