10.3.8 Safety Analysis

All safety analyses will be performed based on the Safety Set.

The safety analysis period is defined as the time between study drug administration and the EOS Visit. Any AE that occurs before study drug administration or after the EOS will not be included in the safety analyses. Safety analyses will be based on descriptive statistics of AEs across cohorts and review of individual subject data such as AEs, safety laboratory data, vital signs, physical examination results, and ECG parameters.

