10.3.8.1 Adverse Events

AEs will be mapped to system organ classes and preferred terms using the MedDRA. AEs will be monitored throughout the study to determine their severity and their potential relationship to the investigational drug. An AE that occurs on or after the first dose of study drug, or an AE that occurs prior to the first dose of study drug, worsens in severity at or after the first dose of study drug, will be considered a post dose-emergent AE.

The incidence of AEs will be summarized by cohort and all subjects and by system organ class, preferred term, severity, and relationship to study drug. Severe and life-threatening AEs, SAEs, and AEs leading to study withdrawal, if any, will also be presented in data listings.

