3.3.2 Safety Variables

Safety will be assessed throughout the study, or at the time points described schedule of assessment (Table 1).

• Adverse events (AEs)

Adverse Event (AE)

An AE is any untoward medical occurrence in a subject after receiving the investigational product and does not necessarily have a clear causal relationship with the investigational drug. An AE can therefore be any unfavorable and unintended sign (e.g., tachycardia, enlarged liver, clinically significant or abnormal laboratory result), subject-reported symptom (e.g., nausea, chest pain), or evidence of any disease activity temporally associated with the use of a study medication, whether or not related to the use of the study medication.

Drug Taken Period Adverse Event

A drug taken period AE will be defined as any AE that emerge during treatment (i.e., AE which started after study drug administration or pre-existed that worsened in severity after study drug administration).

Adverse Events of Special Interest (AESI)

Symptomatic overdose, outcomes of a pregnancy, and LVEF $\leq 30\%$ as determined by local site are considered as Adverse Events of Special Interests (AESIs).

Serious Adverse Event (SAE)

A SAE is an AE that fulfills one or more of the following criteria in the opinion of the investigator or sponsor:

- Results in death;
- is immediately life-threatening (places the subject at immediate risk of death from the event as it occurred);
- Requires subject hospitalization or prolongation of existing hospitalization;
- Resulting in persistent or significant disability or incapability or substantial disruption of the ability to conduct normal life functions.
- Results in a congenital abnormality or birth defect.

Is an important medical event that may not result in death, be life-threatening, or require hospitalization, but may be considered a SAE when, based upon appropriate medical judgment, it may require medical or surgical intervention to prevent one of the outcomes listed above.

• Physical examination findings:

Complete physical examination: general appearance, skin, head and neck, mouth, lymph nodes, thyroid, abdomen, and musculoskeletal, cardiovascular, neurological, and respiratory systems.

Brief physical examination: cardiovascular and respiratory examinations.

- ECG parameters: HR, rhythm, PR interval, QRS interval, QT interval, P wave, QRS complex, T wave morphology, ST segment displacement.

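### The SAP 6.3 algorithm compares calendar dates only, so a Day 1 adverse event with a recorded onset before dosing is counted as a drug-taken-period event

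*SAP*

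**What the plan says.** **The operative rule.** SAP 6.3 contains a table titled as the algorithm for drug-taken-period adverse events. Its first three rows cover a known date of start or of increase in severity, with the stop date known, partial or missing. The first reads "Considered as a drug taken period AE if start date on or after the date of the dose of investigational product (IP"), and the other two apply the same test. No row mentions clock time.

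**The definitions.**
- SAP 3.3.2 defines the drug-taken-period event as an "AE which started after study drug administration or pre-existed that worsened in severity after study drug administration".
- Protocol 10.3.8: "The safety analysis period is defined as the time between study drug administration and the EOS Visit", and "Any AE that occurs before study drug administration or after the EOS will not be included in the safety analyses".
- Protocol 10.3.8.1 defines the post-dose event as "An AE that occurs on or after the first dose of study drug", or an earlier event that worsens at or after that dose.

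**What is collected.**
- Protocol 8.2.1: "AEs will be assessed from the time the subject signs pre-screening ICF through the end of the study". The restriction to procedure-related events covers only pre-screening and screening, which end on Day -2.
- Protocol 8.2.3 records "The date (time, if applicable) that the AE started".

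**Declared departures.** SAP 4.13 explains two differences from the protocol, urea and the PK analysis set. It does not mention this one.

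**The concern.** The definitions run from the act of dosing, while the algorithm runs from the dosing date. They disagree about any event that begins on Day 1 before the capsule is swallowed.

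Such an event can occur. Protocol 7.2 states "On Day 1, vital signs should be collected within 3 h before IMP dosing" and places an ECG in the same interval. Protocol 7.1 schedules a PK blood draw within 60 minutes before dosing, and Protocol 6.4 requires an overnight fast.

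Drug-taken-period events feed the SAP 4.9.1 tables by system organ class and preferred term, by maximum severity and by maximum relationship. These are the main summaries for the secondary objective, safety and tolerability. With cohorts of 8 or 12, one subject is visible in a percentage. SAP 4.9.1 specifies onset date, not time, for the by-subject listing, so the listing need not reveal that a Day 1 event preceded the dose.

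**Working it through.** The plan states no figure on this point, so there is none to reproduce. The check applies the two rules to the same cases and then works out what one case weighs.

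**Step 1: where the rules differ.** The documents give no dosing clock time; 08:00 on Day 1 is assumed for illustration. The events are taken not to worsen later.

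| Onset | SAP 6.3: date on or after dose date | SAP 3.3.2 and Protocol 10.3.8: relative to administration |
|---|---|---|
| Day -1, 20:00 | not counted | not counted |
| Day 1, 07:10 | counted | not counted |
| Day 1, 07:59 | counted | not counted |
| Day 1, 08:30 | counted | counted |

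The rules differ only for onsets on Day 1 before the dose. An earlier event that worsens after dosing is on drug under every definition.

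**Step 2: weight of one subject.** Planned sizes (Protocol 10.1) are 12 in each of Cohorts 1 to 3 and 8 in Cohort 4: 12 + 12 + 12 + 8 = 44. If a subject's only event is misassigned, incidence rises by 100/n points:
- Cohorts 1 to 3: 100/12 = 8.3
- Cohort 4: 100/8 = 12.5
- Overall: 100/44 = 2.3

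These are the weights of any one subject. They do not estimate how much the tables will move.

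**Step 3: how likely a case is.** The documents give no rate of Day 1 pre-dose events. For an assumed per-subject probability p, the chance of at least one in 44 subjects is 1 - (1 - p)^44, and the expected number is 44p:

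| Assumed p | Chance of at least one | Expected subjects |
|---|---|---|
| 0.5% | 20% | 0.2 |
| 1% | 36% | 0.4 |
| 2% | 59% | 0.9 |
| 5% | 90% | 2.2 |

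The range is wide because p is unknown. It shows only that a case is neither certain nor far-fetched.

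**The case against.** The best defence is that SAP 6.3 is headed as imputation for partial dates, and SAP 4.10 cites it only for that purpose. On this view SAP 3.3.2 governs whenever a time is known, and SAP 6.3 is merely silent about time. This does not remove the conflict. The three rows concern known start dates, one of them with both dates complete. They sit in the table that decides which events are drug-taken-period events, and they do not defer to SAP 3.3.2. A programmer following that table would code the date test. The wording in Protocol 10.3.8.1 might be read as a date, but Protocol 10.3.8 expressly excludes events before administration.

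Other parts of the defence stand:
- Any error overcounts on-drug events, the conservative direction for safety.
- Few procedures are involved. Of 23 scheduled PK draws, 1 is pre-dose and 22 are post-dose (13 to 48 h, 9 from Day 7 to Day 75). Events caused by the post-dose draws count as on drug under every definition.
- Protocol 8.2.4 lists temporal relationship among the causality factors, so an investigator should judge a pre-dose onset unrelated. Only a missing assessment defaults to related (SAP 4.9.1).

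A reader might also infer two stronger points that the documents do not support. One is that the event counts in the two previous single-dose studies (Protocol 1.2.2: 4 in 28 subjects, 11 in 16) show a material distortion. None of those events is described as pre-dose or procedural, and event counts are not subject incidence. The other is that the window is equally open after the end-of-study visit. The SAP repeats no upper limit, but Protocol 10.3.8 already excludes later events, Protocol 8.2.1 ends assessment with the study, and the later related deaths and SAEs in Protocol 8.3 are a reporting duty.

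**Conclusion.** The inconsistency is real and small. As written, the known-start rows of SAP 6.3 count a Day 1 event with a recorded pre-dose onset as on drug, contrary to SAP 3.3.2 and Protocol 10.3.8 and 10.3.8.1, and SAP 4.13 does not declare it. The fault is not the date rule itself, which is reasonable when the time is missing, but its use when the time is known.

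The size is conditional: the single-subject shifts above apply only if a case occurs and is that subject's only event. They also assume planned enrolment. Nothing in the documents shows that a misclassification has occurred or that the safety conclusions would change.

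**What to change.** Amend the three known-start rows of the SAP 6.3 algorithm:
1. Date of onset or worsening after the dose date: count, as now.
2. Date equal to the dose date, with a recorded time: compare date and time with the dose date and time, and count only if onset or worsening is at or after dosing.
3. Date equal to the dose date, with no recorded time: keep the date-only rule and state it as the conservative default.

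The cost is three table rows and one programming condition. SAP 4.8.3 already calculates PK parameters from actual time since dose, so the dose time has to be available. Visits and assessments do not change.

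A mandatory onset-time field for Day 1 in the eCRF would help only if data collection is still open, and the correction does not depend on it. Nor does it require a change to the end-of-study limit.
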